8. PHARMACEUTICAL INFORMATION

A list of the adverse events and potential risks associated with Investigational Agent can be found in Section 7.1.

8.1 Investigational Agent

8.1.1 Durvalumab

The Investigational Products Supply section of AstraZeneca/MedImmune will supply durvalumab to the investigator as a 500-mg vial solution for infusion after dilution.

8.1.2 Formulation/packaging/storage

Durvalumab will be supplied by AstraZeneca as a 500 mg vial solution for infusion after dilution. The solution contains 50 mg/mL durvalumab, 26 mM histidine/histidine hydrochloride, 275 mM trehalose dihydrate, and 0.02% (weight/volume) polysorbate 80; it has a pH of 6.0 and density of 1.054 g/ml. The nominal fill volume is 10 mL. Investigational product vials are stored at 2°C to 8°C (36°F to 46°F) and must not be frozen. Drug product should be kept in original packaging until use to prevent prolonged light exposure.

8.1.3 Study drug preparation

For patients weighing > 30 kg a fixed dose of durvalumab at 1.12 g every 3 weeks for 2 cycles will be administered pre-operatively and 1.5 g every 4 weeks for 12 cycles post-operatively.

For patients ≤ 30 kg weight based dosing is required. For the 1.5 g dose a 20 mg/kg dose Q4W would be used and for the 1.12 g dose a 15 mg/kg dose Q3W would be used.

Preparation of durvalumab doses for administration with an IV bag

The dose of durvalumab for administration will be prepared using aseptic technique. Total time from needle puncture of the durvalumab vial to the start of administration should not exceed:

- 24 hours at 2°C to 8°C (36°F to 46°F)
- 4 hours at room temperature

If in-use storage time exceeds these limits, a new dose must be prepared from new vials. Infusion solutions must be allowed to equilibrate to room temperature prior to commencement of administration.

No incompatibilities between durvalumab and polyvinylchloride or polyolefin IV bags have been observed.

A dose of 1.5 g durvalumab for patients >30 kg will be administered using an IV bag containing 0.9% (w/v) saline with a final durvalumab concentration ranging from 1 to 20 mg/mL, and delivered through an IV administration set with a 0.2- or 0.22- μ m in-line filter. Add 30.0 mL of durvalumab (ie, 1.5 g of durvalumab) to the IV bag. The IV bag size should be selected such that the final concentration is within 1 to 20 mg/mL. Mix the bag by gently inverting to ensure homogeneity of the dose in the bag.

A dose of 1.12 g durvalumab for patients >30 kg will be administered using an IV bag containing 0.9% (w/v) saline with a final durvalumab concentration ranging from 1 to 20 mg/mL, and delivered through an IV administration set with a 0.2- or 0.22- μ m in-line filter. Add 22.4 mL of durvalumab (ie, 1.12 g of durvalumab) to the IV bag. The IV bag size should be selected such that the final concentration is within 1 to 20 mg/mL. Mix the bag by gently inverting to ensure homogeneity of the dose in the bag.

Weight-based dosing (for patients \leq 30 kg) will be administered using an IV bag containing 0.9% (w/v) saline with a final durvalumab concentration ranging from 1 to 20 mg/mL, and delivered through an IV administration set with a 0.2- or 0.22- μ m in-line filter. For the 1.5 g dose a 20 mg/kg dose Q4W would be used and for the 1.12 g dose a 15 mg/kg dose Q3W would be used. The Appendix A includes an example of a weight-based dose calculation. Patient weight at baseline should be used for dosing calculations in patients \leq 30 kg unless there is a \geq 10% change in weight. Dosing day weight can be used for dosing calculations instead of baseline weight per institutional standard.

Durvalumab will be administered at room temperature by controlled infusion into a peripheral or central vein. Following preparation of durvalumab, the entire contents of the IV bag should be administered as an IV infusion over approximately 60 minutes (\pm 5 minutes), using a 0.2 or 0.22- μ m in-line filter. Less than 55 minutes is considered a deviation.

The IV line will be flushed with a volume of IV solution (0.9% [w/v] saline) equal to the priming volume of the infusion set used after the contents of the IV bag are fully administered, or complete the infusion according to institutional policy to ensure the full dose is administered and document if the line was not flushed.

Standard infusion time is 1 hour. However, if there are interruptions during infusion, the total allowed time should not exceed 8 hours at room temperature. The table below summarizes time allowances and temperatures.

Durvalumab hold and infusion times

| | |
|--|---|
| Maximum time from needle puncture of vial to start of administration | 4 hours at room temperature, 24 hours at 2°C to 8°C (36°F to 46°F) |
| Maximum time for IV bag infusion, including interruptions | 8 hours at room temperature |

In the event that either preparation time or infusion time exceeds the time limits outlined above, a new dose must be prepared from new vials. Durvalumab does not contain preservatives, and any unused portion must be discarded.

8.1.4 Monitoring of dose administration

Subjects will be monitored before, during and after the infusion with assessment of vital signs at the times specified in the Schedule of Assessment. Subjects are monitored (pulse rate, blood pressure) every 30 minutes during the infusion period (including times where infusion rate is slowed or temporarily stopped).

In the event of a \leq Grade 2 infusion-related reaction, the infusion rate of study drug may be decreased by 50% or interrupted until resolution of the event (up to 4 hours) and re-initiated at 50% of the initial rate until completion of the infusion. For subjects with a \leq Grade 2 infusion-related reaction, subsequent infusions may be administered at 50% of the initial rate. Acetaminophen and/or an antihistamine (e.g., diphenhydramine) or equivalent medications per institutional standard may be administered at the discretion of the investigator. If the infusion-related reaction is Grade 3 or higher in severity, study drug will be discontinued. The standard infusion time is one hour, however if there are interruptions during infusion, the total allowed time from infusion start to completion of infusion should not exceed 4 hours at room temperature. As with any antibody, allergic reactions to dose administration are possible. Appropriate drugs and medical equipment to treat acute anaphylactic reactions must be immediately available. For management of patients who experience an infusion reaction, please refer to the toxicity and management guidelines in Appendix B.

8.1.5 Agent Accountability

The investigator, or a responsible party designated by the investigator, will maintain a careful record of the inventory and disposition of all agents received from Sponsor on a Drug Accountability Record Form (DARF).

9.0 MEASUREMENT OF EFFECT

9.1 Assessment of disease-free survival

All patients will be followed in our thoracic oncology follow-up clinic for disease recurrence using history, physical examination and CT scanning every 6 months for 2 years. This follow-up protocol represents our institutional standard of care. Recurrence will be histologically or cytologically confirmed whenever possible. For the purpose of this trial DFS is defined as confirmed disease recurrence or death from any cause.

9.2 Assessment of clinical response.

All patients will have pre-treatment and post-treatment standard imaging including a positron emission tomography (PET)/computerized tomography scan (PET/CT scan) to determine disease stage and assess response to therapy. All imaging will be downloaded to our imaging data evaluation and analysis laboratory (IDEAL); a state of the art imaging facility operated by the Weill Cornell Department of Radiology. Independent radiologists blinded to treatment allocation will assess tumor shrinkage using conventional RECIST criteria 1.1.

Complete Response (CR): Disappearance of all target lesions. Any pathological lymph nodes (whether target or non-target) must have reduction in short axis to <10 mm.

Partial Response (PR): At least a 30% decrease in the sum of diameters of target lesions, taking as reference the baseline sum diameters.

Progressive Disease (PD): At least a 20% increase in the sum of diameters of target lesions, taking as reference the smallest sum on study (this includes the baseline sum if that is the smallest on study). In addition to the relative increase of 20%, the sum must also demonstrate an absolute increase of at least 5 mm. (Note: the appearance of one or more new lesions is also considered progression).

Stable Disease (SD): Neither sufficient shrinkage to qualify for PR nor sufficient increase to qualify for PD, taking as reference the smallest sum diameters while on study.

9.3 Assessment of pathological response

Major Pathologic Response (MPR): $\leq 10\%$ residual viable tumor in the resected specimen on histopathological examination.

Complete Pathological Response (CPR): The absence of tumor cells in the resected specimen on histopathological examination.

10.0 DATA REPORTING / REGULATORY CONSIDERATIONS

10.1 Data Collection

The data collection plan for this study is to utilize REDCap to capture all treatment, toxicity, and efficacy data for all enrolled patients.

10.1.1 REDCap

REDCap (Research Electronic Data Capture) is a free data management software system that is fully supported by the Weill-Cornell Medical Center CTSC. It is a tool for the creation of customized, secure data management systems that include Web-based data-entry forms, reporting tools, and a full array of security features including user and group based privileges, authentication using institution LDAP system, with a full audit trail of data manipulation and export procedures. REDCap is maintained on CTSC-owned servers that are backed up nightly and support encrypted (SSL-based) connections. Nationally, the software is developed, enhanced and supported through a multi-institutional consortium led by the Vanderbilt University CTSA.

10.2 Regulatory Considerations

All protocol amendments and consent form modifications will be made by the Principal Investigator. AstraZeneca will have the opportunity to review and approve the changes prior to submission of these changes to the local IRB and distribution to participating sites.

10.3 Ethical conduct of the study

The study will be performed in accordance with ethical principles that have their origin in the Declaration of Helsinki and are consistent with ICH/Good Clinical Practice, and applicable regulatory requirements Subject data protection.

11. STATISTICAL CONSIDERATIONS

11.1 Specific Aims

11.1.1 Primary Aim:

The primary aim of this study is to determine that subablative SBRT at a dose of 8Gyx3 given concurrently with neoadjuvant durvalumab will increase the major pathological response (MPR) proportion from an estimated 15% in Arm 1 (Durva alone) to 35% in Arm 2 (SBRT+Durvalumab). A two-group chi-square test with a 0.20 one-sided significance level will have approximately 83% power to detect the difference between the Arm 1 MPR proportion of 0.15 and the arm 2 MPR proportion of 0.35 when the sample size is 30 in each arm.

11.1.2 Secondary Aim:

The first secondary aim of this study is to demonstrate that the use of durvalumab (with/without radiation) is associated with an improvement in the 2-year disease-free survival (DFS) proportion from 75% (historical control) to approximately 88% with the use of the new antibody. The historical control rate was determined from the DFS rate reported by Strauss et al from CALGB 9633, a US based randomized trial of adjuvant chemotherapy versus observation in patients with pathological stages IB and II NSCLC³⁴. The reported 2-year DFS was 68% in the observation arm and 75% in the chemotherapy arm³⁴. Our institutional data are consistent with these results. Among patients in our database who were assigned a clinical stage, there were 215 patients with clinical stages IB and II some of whom received adjuvant chemotherapy. DFS for these 215 patients is shown in Figure 2 and was 75% at 2 years. We did not use DFS reported from other randomized trials since these were international trials and approximately 20-25% of patients enrolled had stage IIIA disease. In our proposed trial, an improvement in DFS by 13% (75% to 88% at 2 years) represents a 17% relative improvement in DFS; a difference that we believe to be both achievable and clinically meaningful. These results will necessarily lead to larger randomized trials for further confirmation.

Another secondary aim is to compare the clinical response between patients receiving the durvalumab alone (Arm 1) and patients receiving the antibody with radiation (Arm 2). Assuming clinical response proportions of 15% and 35% in Arms 1 and 2, respectively, 95% confidence intervals for the clinical response proportions can be constructed to be within $\pm 12.8\%$ and $\pm 17.1\%$ of the observed clinical response proportions in each arm, respectively.

A third secondary aim is to determine the safety of 2 cycles of preoperative durvalumab with and without radiation followed by surgery and adjuvant durvalumab for 12 months post-operatively.

The fourth secondary aim (exploratory) is to compare DFS between the two arms; however, this comparison will be for exploratory purposes only (this comparison will not be statistically powered to detect specific differences between the two arms).

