3.0 PATIENT SELECTION

3.1 Inclusion Criteria

1. Patient has histologically or cytologically proven clinical stages I (tumors > 2 cm), II, and IIIA NSCLC and is considered eligible for surgical resection with curative intent. Patients with 2 primary non-small cell lung cancers are allowed.
2. Measureable disease, as defined by RECIST v1.1.
3. Written informed consent and HIPAA obtained from the subject prior to performing any protocol-related procedures.
4. Age ≥ 18 years at time of study entry
5. Eastern Cooperative Oncology Group (ECOG) performance status of 0 or 1.
6. Adequate normal organ and marrow function as defined below:
 - Haemoglobin ≥ 9.0 g/dL
 - Absolute neutrophil count (ANC) ≥ 1.5 x 10⁹/L (> 1500 per mm³)
 - Platelet count ≥ 100 x 10⁹/L (>100,000 per mm³)
 - Serum bilirubin ≤ 1.5 x institutional upper limit of normal (ULN). This will not apply to subjects with confirmed Gilbert’s syndrome (persistent or recurrent hyperbilirubinemia that is predominantly unconjugated in the absence of hemolysis or hepatic pathology), who will be allowed only in consultation with their physician.
 - AST (SGOT)/ALT (SGPT), and alkaline phosphatase ≤ 2.5 x institutional upper limit of normal (ULN).
 - Serum creatinine CL>30 mL/min by the Cockcroft-Gault formula (Cockcroft and Gault 1976) or by 24-hour urine collection for determination of creatinine clearance:

Males:

$$\text{Creatinine CL (mL/min)} = \frac{\text{Weight (kg)} \times (140 - \text{Age})}{72 \times \text{serum creatinine (mg/dL)}}$$

Females:

$$\text{Creatinine CL (mL/min)} = \frac{\text{Weight (kg)} \times (140 - \text{Age})}{72 \times \text{serum creatinine (mg/dL)}} \times 0.85$$

7. Evidence of post-menopausal status or negative urinary or serum pregnancy test for female pre-menopausal patients. Women will be considered post-menopausal if they have been

amenorrheic for 12 months without an alternative medical cause. The following age-specific requirements apply:

Women <50 years of age would be considered post-menopausal if they have been amenorrheic for 12 months or more following cessation of exogenous hormonal treatments and if they have luteinizing hormone and follicle-stimulating hormone levels in the post-menopausal range for the institution or underwent surgical sterilization (bilateral oophorectomy or hysterectomy).

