11.2 Analysis Plan for Endpoints

11.2.1 Primary Endpoint:

The primary endpoint of the MPR proportion will be calculated for both treatment arms and 80% one-sided confidence intervals will be estimated via binomial proportions. The chi-square test or Fisher's exact test will be used, as appropriate, to compare the MPR proportions between the two arms. We will also generate the odds ratio and a corresponding 95% confidence interval to contrast the difference in MPR proportions between the two arms. Logistic regression will be used to generate the odds ratio and corresponding CI.

11.2.2 Secondary Endpoints:

The first secondary endpoint of 2-year DFS proportion will be calculated for the pooled group of patients (N=60) and a 95% confidence interval will be estimated via binomial proportions. An additional calculation will also be stratified by Arm 1 vs. Arm 2. The chi-square test or binomial exact test, whichever is appropriate, will be used to compare the 2-year DFS proportion in the 60 patients to the historical 2-year DFS proportion of 75%. The chi-square test or Fisher's exact test will be used, as appropriate, to compare the 2-year DFS proportion between the two arms.

The clinical response proportion will be calculated for both treatment arms and 95% confidence intervals will be estimated via binomial proportions. The chi-square test or Fisher's exact test will be used, as appropriate, to compare the clinical response proportions between the two arms.

The safety of durvalumab with and without low dose SBRT in the neoadjuvant setting in NSCLC will be investigated. All AEs in both arms \geq G3 with and without possible or probable attribution to study drug will be tabulated. The frequency of subjects experiencing toxicities will be tabulated for each arm. Toxicities will be assessed and graded according to CTCAE v. 4.0 terminology. Exact 95% confidence intervals around the toxicity proportions will be calculated to assess the precision of the obtained estimates. All analyses will be performed in SAS Version 9.4 (SAS Institute, Inc., Cary, North Carolina) and STATA Version 13.0 (Stata Corporation, College Station, Texas).

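### The 75% historical 2-year DFS is a stage IB–II figure, but section 11.2.2 tests all 60 pooled patients (clinical stage I >2 cm to IIIA) against it, with no stage-matched benchmark or breakdown by stage

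*Combined protocol and SAP*

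**What the plan says.** All references are to the combined protocol and SAP.

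- **Source of the 75%, section 11.1.2.** The first source is a published trial of "adjuvant chemotherapy versus observation in patients with pathological stages IB and II NSCLC", with 2-year DFS of 68% on observation and 75% on chemotherapy. The second is the institutional database, where "there were 215 patients with clinical stages IB and II some of whom received adjuvant chemotherapy" and 2-year DFS was again 75%.
- **Sources set aside, section 11.1.2.** Other randomised trials were not used because "these were international trials and approximately 20-25% of patients enrolled had stage IIIA disease".
- **Target, section 11.1.2.** "an improvement in DFS by 13% (75% to 88% at 2 years) represents a 17% relative improvement in DFS".
- **Who is enrolled, section 3.1 item 1 (also 1.2 and 5.1).** "clinical stages I (tumors > 2 cm), II, and IIIA NSCLC". No limit is placed on the number of IIIA patients.
- **The test, section 11.2.2.** A chi-square or exact binomial test is used "to compare the 2-year DFS proportion in the 60 patients to the historical 2-year DFS proportion of 75" per cent. The only breakdown of the 2-year proportion is by arm: "An additional calculation will also be stratified by Arm 1 vs. Arm 2". The Kaplan–Meier analyses are also split by arm only.
- **Status.** The aim is secondary, and section 11.1.2 adds: "These results will necessarily lead to larger randomized trials for further confirmation".

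**The concern.** Both sources of the null are confined to stages IB and II. The population tested is wider at both ends: it takes in IIIA, and stage I tumours over 2 cm that fall below IB. The plan treats a 20–25% share of IIIA as one reason why a benchmark is unsuitable, yet it leaves its own IIIA share open and does not comment on the difference.

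This matters because both arms receive durvalumab. The randomised comparison therefore cannot show what durvalumab itself does to DFS, and the hypothesis in section 1.4.3 that it improves DFS over historical controls rests on this external figure alone. If the DFS that the enrolled mix would have had without durvalumab is below 75%, a real gain can be missed. If it is above 75%, a favourable stage mix can be read as a drug effect.

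**Working it through.** **The plan's own figures.** The absolute gain is 88 − 75 = 13 points, and the relative gain is 13/75 = 17.3%. Both match section 11.1.2. (Section 1.2 gives the target as 89%; 88% is used here.) No significance level, sidedness or power is stated for this test, so an exact binomial test with upper tail 0.025 is assumed below.

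**The test as planned.** With n = 60 and null 0.75, the smallest count c with P(X ≥ c | 0.75) ≤ 0.025 is c = 52, and P(X ≥ 52 | 0.75) = 0.021. At a true DFS of 88%, power is P(X ≥ 52 | 0.88) = 0.710.

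**If the no-effect DFS of the enrolled mix is not 75%** (cut-off held at 52/60):

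| True no-effect DFS | False success | Power, 13-point gain |
|---|---|---|
| 70% | 0.2% | 29% |
| 75% | 2.1% | 71% |
| 78% | 6.6% | 91% |

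**A mix with IIIA patients.** The IIIA share s is set to 20% or 25%, the share that the plan quotes for the trials it set aside (12 to 15 of 60). The documents give no IIIA DFS, so d = 45%, 55% or 65% is assumed, with 75% in everyone else.

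- No-effect DFS = s·d + (1 − s)·0.75.
- Flat model: DFS on durvalumab = no-effect DFS + 0.13.
- Common hazard ratio: ln 0.88 / ln 0.75 = 0.444, applied in each stage as DFS^0.444. This turns 75% into 88.0%, and 45%, 55% and 65% into 70.1%, 76.7% and 82.6%.

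| IIIA share, IIIA DFS | No-effect DFS | False success | Power, flat 13 points | Pooled DFS, common hazard ratio | Power, common hazard ratio |
|---|---|---|---|---|---|
| 20%, 45% | 69.0% | 0.1% | 22% | 84.4% | 40% |
| 20%, 55% | 71.0% | 0.4% | 36% | 85.7% | 51% |
| 20%, 65% | 73.0% | 0.9% | 53% | 86.9% | 62% |
| 25%, 45% | 67.5% | 0.1% | 15% | 83.5% | 33% |
| 25%, 55% | 70.0% | 0.2% | 29% | 85.2% | 46% |
| 25%, 65% | 72.5% | 0.7% | 49% | 86.6% | 59% |

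Power is 15–53% under the flat gain and 33–62% under the common hazard ratio, against 71% if the benchmark were right.

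**A mix with smaller stage I tumours and no IIIA.** Assume 20–30% of patients with a no-effect DFS of 85–90%, and 75% in the rest. The no-effect DFS then runs from 0.20 × 85 + 0.80 × 75 = 77.0% to 0.30 × 90 + 0.70 × 75 = 79.5%. False success at 52/60 runs from 4.6% to 10.8%. The mismatch now points the other way.

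**The case against.** The strongest reply is that an imperfectly matched external control is an ordinary limitation of a phase II secondary aim. Section 11.1.2 speaks of an association and defers to larger randomised trials. It also uses the 75% of the chemotherapy arm rather than the 68% of the observation arm, which is the more demanding choice. A 95% confidence interval is planned, so a reader can compare the result with another null. All of this stands, and it keeps the point at the level of a secondary aim. It does not supply a matched null or a result by stage, and choosing another null after DFS is known invites bias in an open-label trial whose monitoring committee reviews interim efficacy (section 7.4).

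A second reply is that every stage-specific DFS above is assumed. That is correct. The documents give neither stage-specific DFS nor an expected stage mix, and the one borrowed share, 20–25% IIIA, describes other trials. The size of the power loss also depends on the effect model: the flat 13-point gain is harsher than the common hazard ratio, so both are shown. The mismatch between the sources and the tested population is a matter of text and does not depend on these values.

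A reader might infer that 75% is simply too high because IIIA patients are enrolled. The documents do not support that, since smaller stage I tumours pull the other way and the mix is unknown.

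**Conclusion.** The point holds as a mismatch between benchmark and population. The 75% comes from stage IB–II patients, it is applied to a pooled group running from clinical stage I over 2 cm to IIIA, and section 11.2.2 plans nothing that would separate stage mix from a durvalumab effect. The textual finding is certain. Its consequence is conditional: IIIA patients would be expected to make 75% too high a bar, and stage I tumours below IB too low a bar. Under the assumed test, false success is 0.2%, 2.1% or 6.6% at a no-effect DFS of 70%, 75% or 78%. With the assumed IIIA mixes, power is 15–53% (flat gain) or 33–62% (common hazard ratio).

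This does not show that 75% is wrong for the patients who will be enrolled. Nor does it justify withholding any claim of improvement until the result holds against a whole range of alternative nulls: stage counts cannot set such a range without stage-specific DFS, and the rule would change the plan's decision criterion. The randomised comparison of major pathological response is unaffected.

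**What to change.** Keep the pooled test against 75%. Before DFS is analysed, amend section 11.2.2 to prespecify two supporting analyses:

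1. 2-year DFS in the stage IB–II subset against 75%, with DFS and its 95% confidence interval reported descriptively for the other enrolled stages.
2. Where the institutional database holds the other enrolled stages with DFS follow-up, the pooled DFS against a benchmark standardised to the enrolled stage mix, allowing for the benchmark's sampling error. Fix this benchmark without sight of trial DFS outcomes.

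State in section 11.1.2 and in the report that 75% is a stage IB–II benchmark and that the pooled comparison may reflect stage mix.

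**Cost.** A database query, a few lines of text and modest extra analysis; no more patients, and no change to the planned test. The supporting analyses are imprecise:

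- The IB–II subset has low power for 75% against 88%. At upper tail 0.025, with 30, 40 or 45 patients, the cut-offs are 28, 36 and 40, and power is about 28%, 47% and 54%.
- A benchmark from 215 patients has a standard error of √(0.75 × 0.25/215) = 2.95 points, or about ±5.8 points at 95% (complete 2-year follow-up assumed). A two-sample comparison of 60 against 215 (pooled z test, 75% against 88%) has about 59% power, before any variance added by standardising.
- The documents do not show that the database covers IIIA and the smaller stage I tumours, so the second analysis may not be possible. The first analysis and the added statement would then carry the point.
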